9 CHANGES TO PLANNED ANALYSIS FROM STUDY PROTOCOL

The following changes were agreed upon

1. Sites were changed from random effects to region (US or Europe) which is being treated as a fixed effect.
2. LOCF was excluded from imputation methods.
3. The ranked outcome for adjustment for multiplicity was changed. The ItchyQoL measure & the PROMIS scale were excluded from the ranking and replaced with PAS (5a)
4. The analyses for prohibited medication were changed to set all efficacy outcomes to missing from the date of ingestion of the prohibited medication. Previously, missing outcomes were set = non-responders.
5. A new set of simple multiple imputation models were added to assess the impact of missing efficacy measures due to the use of prohibited medications.

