5. Use PROC MIANALYZE to combine the efficacy output to get a single estimate from all the imputed data sets.

Step 1. Checking missing data patterns

For this study, the missing data patterns will be checked by treatment and visits 3 to 5.

There are 3 steps to this process:

Create dataset for efficacy measure including visits from baseline to week 14

```
data mi_chk1; set datax;
where param="" and paramcd="" and dtype="" and 3 <= visit <=5;
run;
```

Transpose dataset to display each visit as one column:

```
proc sort data = mi_chk1; by treatment_id;
proc transpose data=mi_chk1 out=mi_chk2 prefix="";
by treatment_id;
id avisitn;
var aval;
run;
```

Use PROC MI with the NIMPUTE=0 option to create the "Missing Data Patterns" table for the specified variables:

```
ods output MissPattern=missp;
proc mi data=mi_chk2 NIMPUTE=0;
  by treatment;
  var visit3 – visit5;
run;
/*Add baseline to estimate change from baseline*/
```

```
proc sort data = mi_chk1; by id; data base; set mi_chk1 (Keep = id base country); by id; if first.id;
run;
proc sort data = mi_chk2; by id;
proc sort data = base; by id;
data mi_chk2; merge mi_chk2 base; by id;
run;
```

Step 2: Impute non-monotonic / intermittent data – leaving only monotone missing data.

Fill in the intermittent missing data using the following code.

```
proc sort data = mi_chk2; by treatment;
proc mi data=mi_chk2 seed=12345 NIMPUTE=50 out=MI;
by trt01pn;
mcmc impute=monotone;
var Visit3 – Visit5;
run;
```

Step 3. Use monotone regression to impute monotone missing data & create multiply imputed data sets.

Here the non-missing values for subjects in the control group are used to impute values for the subjects with missing values in the control group and similarly for the subjects in the active treatment group.

**Visit 3 values are imputed using baseline value and treatment;
visit 4 values are imputed using baseline, treatment and visit 3 & so on.**

```
proc sort data = mi; by _Imputation_;
proc mi data=mi out=mi_reg seed=54321 nimpute=1;
by _Imputation_;
var trt01pn base v3 v4 v5;
class trt01pn;
monotone regression;
run;
```

Convert the data set from a horizontal dataset, i.e. one row per subject to a vertical data set, i.e., multiple rows per subject.

```
Data mi_reg1; set mi_reg;
Visit = 1; WINRSA=base; output;
Visit = 2; WINRSA=v3; output;
visit = 3; WINRSA=v4; output;
visit = 4; WINRSA=v5; output;
drop v3 v4 v5;
run;
```

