Step 4. Run the efficacy analyses (PROC GENMOD, PROC MIXED) on the multiply imputed data sets.

Create variables needed for the 50 data sets, e.g. RESP, Pooled Site, treatment coded as (0-Placebo,1-Treatment) etc.

1. Fit the models on the 50 imputed data sets by _Imputation_.

```
proc sort data = mi_reg1;
by _imputation_ visit trt;
```

```

ods select none; /*suppress printing the output*/

proc genmod data=winrsa descending; where avisitn ge 3;
class usubjid avisitn trt posite ;
model resp = trt avisitn avisitn*trt posite base
/dist=binomial;
repeated subject=usubjid / withinsubject=avisitn
type=un;
lsmeans trt*avisitn /cl ilink diff oddsratio;
Ods output diff=diff lsmeans=lsm ;
run;

```

Step 5. Combine estimates of the 50 GENMOD models to create an overall estimate and a relative efficacy score.

Due to the finicky nature of PROC MIANALYZE, the suggestion is to produce output to one effect at a time. This can be programmed in a macro.

Run three separate instances of GENMOD to get the effect for the interaction first, then the treatment & then visits

MIANALYZE cannot handle too many effects and too many variables in the input data sets, so subset to the needed effects. For the interaction, choose the estimate for the same visit but different treatments. That is what the next two statements do.

```

data diff_mi_nw; set diff_mi; where visit = _visit and trt ne _trt;run;
data diff_mi_nw2; set diff_mi_nw (keep = _imputation_ estimate stderr effect); run;

```

The data set diff_mi_nw2 is then fed into the Proc MIANALYZE:

```

proc mianalyze parms=diff_mi_nw2; /*where _imputation_ le 4;
modeleffects treatment*visit ;
run;

```

Since this is GENMOD the results should be presented as odds ratios (ORs). The final estimate & the SEs should be exponentiated to create the ORs.

Also fit the continuous ITCH score using Proc Mixed.

```

ods select none;
proc mixed data = mi_reg1; by _Imputation_ ;
class variables;
Model (Continuous endpoint) = Treatment, Baseline Vars, Time, Treatment * Time/solution
covb;
repeated ID/ type = cs subject = ID(treatment)
lsmeans Interaction Term/diff cl;

```

```
ods output Diffs=diff_mi LSMEANS=lsm_mi;
run;
ods select all;
```

Subset the data set to be input into MIANALYZE.
data diff_mi_nw; set diff_mi (keep = _imputation_
estimate stderr effect probt);
run;

```
proc mianalyze parms=diff_mi_nw;
modeleffects effect of interest (e.g., treatment, Visit or interaction but to be done one at a time);
run;
```

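### SAP 12.3 Step 3 imputes both arms from one regression, contrary to its own text, and omits the region term that the responder model adjusts for

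*SAP*

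**What the plan says.** **Step 3 code.** The predictor list is "var trt01pn base v3 v4 v5", with "class trt01pn". The procedure is processed by imputation number only, so each imputed data set gets one regression per visit, covering both arms. The Tipping Point Analysis part of SAP 12.3 repeats the same imputation.

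**Step 3 text.** Just above the code the SAP says that "the non-missing values for subjects in the control group are used to impute values for the subjects with missing values in the control group". It states the same rule for NAL ER. The next sentence describes something else: "Visit 3 values are imputed using baseline value and treatment".

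**Step 2.** The filling of intermittent gaps is run separately by arm.

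**Region.** Country is kept and merged with baseline before Step 2, but it appears in no PROC MI variable list. The Step 4 responder model is "model resp = trt avisitn avisitn*trt posite base". SAP 9, item 1, explains the site term: "Sites were changed from random effects to region (US or Europe) which is being treated as a fixed effect". The MMRM for continuous endpoints (SAP 8.6.3) has treatment, visit, their interaction and baseline, and no region.

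**The concern.** An imputation model should contain at least the covariates of the analysis it feeds. Without region, imputed scores carry no regional difference beyond what the earlier scores convey, and the responder model then adjusts for region on those scores. Pooling the arms makes NAL ER dropouts follow slopes and a spread partly learned from placebo subjects, which the first Step 3 sentence says will not happen. A programmer has two instructions that give different numbers.

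The stake is modest but real. The SAP leaves missing Week 14 responses missing under MAR (7.4.1, 8.6), where protocol 13.4.6.1 counted them as non-response. More therefore rests on the imputation analyses, and SAP 8.6 wants them to guard against false positive findings. An error that favours NAL ER works against that aim.

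**Working it through.** **Inputs.** The plan gives no figure for this point. The design assumptions used for scale can be checked: 25% versus 45%, 90% power, two-sided 0.05 (SAP 5).

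n per arm = [1.960 × √(2 × 0.35 × 0.65) + 1.282 × √(0.25 × 0.75 + 0.45 × 0.55)]² / 0.20² = 117.4, so 118 per arm or 236 in total. SAP 5.2 states 234 without site and 240 with it, so the inputs agree.

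No dropout rate is stated. In TR03 (protocol 13.1), 12 of 18 subjects on NAL ER 162 mg and 20 of 22 on placebo completed, so non-completion was 6/18 = 33% and 2/22 = 9%.

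**Pooled slopes, by algebra.** With an arm main effect, least squares passes through each arm's observed mean. For one imputed visit, the bias in arm a's mean is

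mₐ × (β_pooled − βₐ) × (x̄_missing,a − x̄_observed,a),

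where m is the fraction missing, β the slope on the earlier score and x̄ its mean. It is zero when the arms share a slope, however far apart their means. It is also zero when dropout is unrelated to the earlier score. Responder proportions depend on spread too, so wrong slopes or variances can still move them.

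**Omitted region, by algebra.** If region shifts the next score by δ given the earlier scores, equally in both arms, the bias in the treatment difference is approximately

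δ × (p_NAL − p_placebo),

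where p is the region's share among subjects still observed. It vanishes if δ = 0, or if the regional mix of observed subjects is the same in both arms.

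**Simulation.** 300,000 subjects per arm, with baseline and Weeks 6, 10 and 14, monotone MAR dropout and sequential regression imputation. Bias is against the full data. A negative mean bias overstates the NAL ER benefit. Slopes, region effect (0.5 points per visit) and regional dropout odds ratio (3) are assumptions.

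| Scenario | Dropout % placebo/NAL ER | True responder difference | Step 3 code: mean bias | Step 3 code: responder bias (points) | Step 3 code: log OR bias | By arm with region: responder bias |
|---|---|---|---|---|---|---|
| A. Mean courses differ, slopes equal | 14.0/33.6 | 22.54 | +0.001 | −0.02 | −0.001 | +0.07 |
| B. Slopes 0.6/0.9, dropout depends on prior score | 15.5/33.8 | 26.48 | −0.124 | +1.59 | +0.068 | +0.14 |
| B2. Slopes 0.6/0.9, dropout unrelated to score | 13.3/30.7 | 26.69 | +0.004 | −0.54 | −0.027 | +0.03 |
| C. Region effect, same regional dropout in both arms | 24.1/24.1 | 21.38 | +0.003 | +0.14 | −0.023 | −0.03 |
| C2. As C, more NAL ER dropout | 14.6/32.5 | 21.15 | −0.038 | +0.97 | +0.016 | −0.03 |
| D. Region effect, regional dropout in NAL ER only | 13.3/32.3 | 21.33 | −0.064 | +1.42 | +0.039 | +0.01 |
| D2. As D, region does not predict outcome | 13.5/32.4 | 22.35 | +0.002 | +0.04 | +0.001 | +0.05 |
| E. Region effect in NAL ER only, regional dropout in both arms | 14.9/32.4 | 22.52 | −0.068 | +1.44 | +0.051 | −0.01 |
| F. Region effect, dropout not regional | 13.5/30.7 | 21.36 | +0.003 | −0.07 | −0.022 | −0.08 |

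Scenarios A, C and D2 behave as the algebra predicts. In a separate run, also 300,000 per arm, in which only the variances differed by arm, the responder difference was 19.7 points pooled against 20.4 by arm, so pooling understated NAL ER by 0.7.

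**Is half the change enough?** No. Adding region to the pooled regression leaves +1.60 points in B and +1.02 in E. Running by arm without region leaves +1.46 in D and +1.46 in E.

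**Scale.** At 180 per arm the standard error of the responder difference is √[(0.1875 + 0.2475)/180] = 4.9 points. The largest bias is 1.59/4.9, about one third of a standard error.

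**The case against.** The best reply has four parts.

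- **The code is only guidance.** SAP 12.3 says it is not the exact code. It also says its processes and principles need to be followed, and which covariates enter and whether arms are pooled are matters of that kind.
- **The text also supports the code.** The sentence on using baseline and treatment matches it. That is fair, but it leaves two adjacent descriptions that cannot both be carried out.
- **Bias needs several conditions at once, and no document says that they hold.** This stands. A reader might infer that imputed differences are biased whenever dropout varies by region or the arms follow different courses. Scenarios A and D2 show no material bias in either case, and C shows only 0.14 points with slight attenuation of the log odds ratio.
- **Step 3 is not the planned robustness test.** This also stands. A reader might infer that the check on MAR itself fails. SAP 7.4.1 and 8.6 assign that check to MNAR methods, control-based imputation and the tipping point. Simple multiple imputation assumes MAR, and SAP 9, item 5, adds it for data missing because of prohibited medication. The control-based regressions exclude observed NAL ER values at the visit being imputed, so pooling of arms does not reach them. The tipping-point analysis does start from the Step 3 imputation, but then shifts imputed values by up to one SD in both directions.

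The disagreement with Step 2 is minor in effect, since SAP 8.6 expects few intermittent gaps.

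**Conclusion.** The inconsistency is established from the text: Step 3 and its tipping-point copy share slopes and residual variance across arms, against a sentence of their own, and leave out the region term of the responder model. The consequence is conditional. Bias requires slopes or residual variances that differ by arm, or a region effect on later scores given earlier ones together with dropout or a region effect that differs by arm. Under assumed adverse inputs the error is about 1 to 1.6 responder points, mostly favouring NAL ER. The direction is not uniform: B2 and the variance-only run went the other way by 0.5 to 0.7 points.

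The primary analysis is untouched. The MMRM has no region term, so the region mismatch does not extend to it. This is a low-priority correction, worth making because it costs little and removes a choice from the programmer.

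**What to change.** In Step 3 and in the tipping-point imputation:

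1. Sort and run by imputation number and TRT01PN, and drop TRT01PN from the VAR list.
2. Add the analysis model's two-level region term to CLASS and VAR.
3. Reword the sentence that lists treatment as a predictor, so that text and code agree.

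For consistency, add region to the control-only regressions of the control-based imputation; no calculation was run for that step. Name one region variable throughout, because the SAP calls the term USA versus other (8.5.1.1), country (8.6) and US or Europe (9).

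Imputing by arm with region kept responder bias within 0.15 points and log odds ratio bias within 0.006 in all nine scenarios. The cost is a few words of code and slightly larger imputation variance, because fewer subjects inform each arm's regression. At about 180 per arm that increase should be small.

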8.5.1.2 Mixed model repeated measures analysis

A mixed model repeated measures analysis using ‘direct likelihood’ will be performed for continuous efficacy outcomes. The SAS procedure PROC MIXED will be used. The preferred model will include the fixed effects of treatment, visit, treatment-by-visit interaction, and the baseline value of the endpoint variable as a covariate. An unstructured matrix for the variance-covariance will be used. The denominator degrees of freedom will be calculated according to the Kenward-Roger method.

In case of non-convergence of the preferred model or memory issues, the following back-up models are defined:

1. The same as the preferred model, but the Kenward-Roger method will be replaced by Satterthwaite approximation.

2. The same as the preferred model, but with handling of the selection of the covariance structure for the final model in a hierarchical fashion, with the order being Toeplitz, AR (1), and compound symmetry, respectively.

The second back-up model will only be used if the first back-up model does not converge or has memory issues.

The model will provide least-squares mean estimates, standard errors, two-sided 95% confidence intervals and p-values (where applicable) for mean change at all visits between treatments (NAL ER vs. placebo).

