8.6.3 Analysis of secondary efficacy endpoints

All secondary endpoints will be analyzed using the mITT population.

MMRM without imputation for missing data:

The following secondary efficacy endpoints will be analyzed using a mixed model for repeated measures (MMRM):

- The mean change in 7-day average WINRS from baseline to Week 14 for the NAL ER treatment arm versus the placebo arm;
- The mean change in ItchyQoL from baseline to Week 14 for the NAL ER treatment arm versus the placebo arm;
- The mean change in sleep disturbance (PROMIS Sleep Disturbance Short Form 8a) from baseline to Week 14 for the NAL ER treatment arm versus the placebo Arm.

The analysis of change from baseline to week 14 will be performed utilizing all observed data for visits up to and including Week 14, without imputation for missing data. The model used for this analysis will include the fixed effects of treatment, visit, treatment-by-visit interaction, and baseline value. An unstructured variance-covariance matrix will be used in the analyses. The comparison of interest is the treatment difference at Week 14. The model will provide least-squares mean estimates, standard errors, two-sided 95% confidence intervals and p-values for mean change at all time points between treatments (NAL ER vs. placebo) for ItchyQoL (total score and subscales: symptoms, functional limitations, emotions) and PROMIS. The same statistics will be provided for WI-NRS, except for the p-values.

Sample SAS code:

```
PROC MIXED data=xxxx;
  CLASS visit treatment subjid;
  MODEL CHG = treatment visit treatment*visit baseline/solution DDFM=KENWARDROGER;
  REPEATED visit / type=un subject=subjid;
  LSMEANS treatment*visit / pdiff CL;
  ODS output Diffs=outdata1 LSMeans=outdata2;
RUN;
```

Sensitivity analyses: MMRM with imputation for missing data

We will use the imputation methods described above for the primary efficacy endpoints to assess the sensitivity of missing data on inference regarding the secondary endpoints. Since these are continuous measures, we will use the delta methods described above.

Summary for Categorical Endpoints:

The count and percentage will be provided for the following endpoints:

- Change in PAS as assessed by the percentage of subjects having a 1-category improvement in the percentage of prurigenous lesions with excoriations/crusts (item 5a) from baseline to Week 14 for the NAL ER treatment arm versus the placebo arm;

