Control-Based Imputation.
STEPS 1-4 ARE EXACTLY AS DESCRIBED ABOVE.

The imputation of missing values is done one visit at a time.

The difference between this process and the simple multiple imputation above is primarily in the data management step where a dataset is created with all control subjects and only those trt = NALER subjects who have missing values for visit, one visit at a time.

Below is the suggested approach.

In this case use v3, v4 & v5. After the intermittent missing data is filled in, one would expect all v3 to be filled in & only v4 & v5 to be missing.

This is also a way to check & make sure that the data is behaving as expected.

- Step 1. Create two separate data sets, i.e., one with just control subjects and one with just NALER subjects;
- Step 2. Create a subset NALER data to include only those who have missing values for visit 4;
- Step 3. Set the Control data set and the dataset with V4 missing by _Imputation & usubjid.

Now, the dataset has all of the control subjects and only the NALER subjects with v4 missing in this data set.

Sample Program:

```

data control_mi; set mi; where trt = 0; run;
data trt_mi; set mi; where trt = 1;
data v4_trt_mi; set trt_mi; where v4 = .; run;
proc sort data = control_mi; by _imputation_usubjid;
proc sort data = v4_trt_mi; by _imputation_usubjid;
data mi_v4; set v4_trt_mi control_mi; by _imputation_usubjid;
run;

```

Then use monotone regression to impute the v4 values.

```

proc sort data = mi_v4; by _Imputation_;
proc mi data=mi_v4 out=mi_reg_v4 seed=54321 n impute=1;
by _Imputation_;
var base v3 v4
monotone regression (v4);
run;

```

Repeat for v5.

Then merge the data set back to include the full treatment = NALER data set with the non-missing & imputed values together. Set the Trt = 1 & trt = 0 data sets by _Imputation_ & usubjid

2. **Convert the data set from a horizontal dataset, i.e. one row per subject to a vertical data set, i.e., multiple rows per subject.**

```

Data mi_reg1; set mi_reg;
Visit = 1; WINRSA=base; output;

```

```
Visit = 2; WINRSA=v3; output;
visit = 3; WINRSA=v4; output;
visit = 4; WINRSA=v5; output;
drop v3 v4 v5;
run;
```

Create required variables needed in these 50 data sets, e.g. RESP, Pooled Site, treatment coded as (0,1) etc.

Run Proc GENMOD or Proc Mixed
Run Proc MIANALYZE

Tipping Point Analysis.

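### The Appendix 12.3 PROC MIXED template for imputed data prints compound symmetry, where SAP 8.5.1.2 and 8.6.3 specify an unstructured matrix over visits

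*SAP*

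**What the plan says.** **Main analysis.** SAP 8.5.1.2 sets the general method for continuous efficacy outcomes: "An unstructured matrix for the variance-covariance will be used". If the preferred model fails to converge or runs out of memory, the first back-up changes only the degrees-of-freedom method. The second changes the covariance structure, "with the order being Toeplitz, AR (1), and compound symmetry, respectively". SAP 8.6.3 repeats the choice for WI-NRS change, ItchyQoL and PROMIS: "An unstructured variance-covariance matrix will be used in the analyses". Its sample code agrees: "REPEATED visit / type=un subject=subjid".

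**Imputed data.** Step 5 of Appendix 12.3 says "Also fit the continuous ITCH score using Proc Mixed" and gives a PROC MIXED template with the line "repeated ID/ type = cs subject = ID(treatment". No convergence condition is attached, and there is no robust-variance or group option. The template reads the long data set built in Step 3, whose first row per subject is "Visit = 1; WINRSA=base; output". The GENMOD step just before it restricts the visits used; the MIXED step does not.

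**Other imputation runs.** The control-based section says "Run Proc GENMOD or Proc Mixed" without naming a covariance structure. The tipping point section sends the programmer back to the same modelling step.

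Neither SAP Section 9 (changes from protocol) nor Section 11 (version history) mentions or explains a different covariance for imputed data.

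**The concern.** A missing-data sensitivity analysis should differ from the main analysis only in its missing-data assumption. Here the printed code would change the covariance model as well, so a difference between the two results could not be put down to the missing data alone.

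The change also bears on the quantity of interest. With completed data and a treatment-by-visit term, compound symmetry leaves the Week 14 treatment estimate essentially unchanged but replaces the Week 14 variance with the average over visits. A baseline row that is both response and covariate has little residual variance and pulls that average down. If variance rises towards Week 14, the interval is too narrow and the sensitivity result looks firmer than it is.

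Convergence is an unlikely reason to prefer the simpler structure. After imputation nothing is missing, and Appendix 12.3 uses only three post-baseline visits (ADQS) or four (ADEFF).

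**Working it through.** The plan states no SD by visit, Week 14 standard error or power for the continuous endpoints, so there is no figure of its own to reproduce. The SD patterns, correlation, baseline distribution and between-imputation share below are assumptions. As printed, the REPEATED line does not index visits, so the check takes the natural reading: compound symmetry across visits.

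**1. Completed data.** Let r be the Week 14 standard error under compound symmetry divided by that under an unstructured matrix.

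r = sqrt(mean of the visit variances / Week 14 variance); coverage of a nominal 95% interval = 2Φ(1.96 r) − 1.

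- Growing, SDs 2.0, 2.3, 2.5: mean variance = (4.00 + 5.29 + 6.25)/3 = 5.18; r = sqrt(5.18/6.25) = 0.910; coverage 92.6%.
- Falling, the same SDs reversed: r = sqrt(5.18/4.00) = 1.14, so the standard error is too large.
- Growing, with a baseline row of assumed residual SD 0.6: mean variance = (0.36 + 15.54)/4 = 3.975; r = sqrt(3.975/6.25) = 0.797; coverage about 88%.

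**2. After Rubin pooling.** If λ is the between-imputation share of the true total variance, the ratio becomes sqrt((1 − λ)r² + λ). With λ = 0.3:

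- 0.910 becomes sqrt(0.7 × 0.8288 + 0.3) = 0.938; coverage about 93.4%.
- 0.797 becomes sqrt(0.7 × 0.636 + 0.3) = 0.863; coverage about 91%.

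**3. Simulation on completed data with no treatment effect.** There were 180 subjects per arm (the protocol's 360 in total), visits at Weeks 6, 10 and 14, AR(1) correlation 0.7, and baseline uniform from 7 to 10. Compound symmetry had 4000 runs and unstructured 1500. Simulated columns labelled ratio give model standard error over empirical SD; rejection rates are at nominal 0.05.

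| SDs, Weeks 6:10:14 | r (formula) | with λ = 0.3 | CS ratio, no baseline row | rejection | CS ratio, baseline row kept | rejection | UN rejection |
|---|---|---|---|---|---|---|---|
| constant | 1.00 | 1.00 | 1.00 | 0.049 | 0.87 | 0.090 | 0.053 |
| 1:1.1:1.2 | 0.919 | 0.944 | 0.94 | 0.067 | 0.81 | 0.112 | 0.043 |
| 1:1.25:1.5 | 0.844 | 0.894 | 0.84 | 0.099 | 0.73 | 0.158 | 0.054 |
| 1:1.5:2 | 0.777 | 0.850 | 0.78 | 0.125 | 0.68 | 0.182 | 0.049 |
| 1:0.9:0.8 | 1.130 | 1.092 | 1.13 | 0.025 | 0.98 | 0.055 | 0.051 |

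The simulation agrees with the formula. Keeping the baseline row makes the standard error too small even when post-baseline variance is constant: with almost no residual variance in that row, sqrt(3/4) = 0.87. Under falling variance the two errors nearly cancel (0.98). The unstructured matrix holds its level in every pattern, with ratios of 0.99 to 1.03.

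**The case against.** **The appendix is guidance.** It says that it does not supply the exact code. The MIXED block cannot run: it has placeholders for the class variables and the endpoint, commas in the MODEL statement and a missing semicolon. SAP 8.6.3 calls the imputed analysis an MMRM, directly under text that specifies an unstructured matrix. This stands, so the finding is that template and body disagree, not that the final program will use compound symmetry. But the appendix also presents itself as the principles to follow, and compound symmetry is the only structure that it names for PROC MIXED.

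**The line belongs to simple imputation of the itch score.** The control-based section carries over Steps 1 to 4 and names no structure; the tipping point text names none either. Extending compound symmetry to ItchyQoL and PROMIS is therefore inference, though the template's endpoint is generic and no other MIXED code is given for those runs. For WI-NRS, 8.6.3 reports no p-value, so there the interval is what would be affected.

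**The baseline row may never reach the model.** Appendix 12.3 lists only post-baseline visits for the imputation, and a competent programmer might drop the row. That is fair, and it is why the 20% understatement with 88% coverage should not be the headline. It needs that row to be kept and an assumed residual SD of 0.6.

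**The direction is not fixed.** A reader might infer that the intervals are simply too narrow. The documents do not support that: no SDs by visit are given, constant variance without the baseline row has no effect, and falling variance reverses the sign. Growth from baseline is plausible for WI-NRS, because inclusion criterion 5 requires a baseline mean of at least 7 while later scores can span 0 to 10. That does not show growth between Weeks 6 and 14.

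**Conclusion.** The contradiction is in the text and has no stated reason. Its consequence is conditional: if the template is followed, the Week 14 standard error in the imputed sensitivity analyses reflects a variance averaged over visits.

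Across the assumed growing patterns with the baseline row dropped, the ratio runs from about 0.78 to 0.92 on completed data, and from 0.85 to 0.94 with a 30% between-imputation share. The example SDs of 2.0, 2.3 and 2.5 fall inside both ranges. Keeping the baseline row lowers the ratio in every pattern tested. These sizes depend entirely on assumed SDs.

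A reader might go further and infer that the main results or the error rate of the fixed testing sequence are compromised. They are not: the main MMRM is specified with an unstructured matrix and does not use this code. This is a minor point, worth correcting because it is cheap and because it keeps the sensitivity analyses comparable with the main one.

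**What to change.** In Appendix 12.3:

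- Replace the REPEATED line with `repeated visit / type=un subject=usubjid`, and state that the back-up order of 8.5.1.2 applies if the model does not converge.
- Exclude the baseline row from the response data before PROC MIXED, keeping baseline as a covariate.
- State that the same model applies to the continuous endpoints in the control-based and tipping point runs.

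The template's fixed effects (treatment, baseline, time and their treatment interaction) already match 8.5.1.2. The cost is a few lines of guidance code, with no new data and no change to the main analysis. If compound symmetry was intended, SAP Section 9 should say so and give the reason.
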